## **2.0 STUDY OBJECTIVES**

### **2.1 Primary Objectives**

Our primary objectives are to quantify outcomes of patients with osseous metastases treated via the STAT RT workflow. Specifically, we are plan to:

- 2.1.1** Estimate the response to palliative radiation as defined by International Bone Metastases Consensus Group using the BPI and OMED to categorize into Complete Response, Partial Response, Pain Progression, and Stable Pain after receiving treatment via the STAT RT workflow.
- 2.1.2** Estimate the change in the patient's quality of life and function as scored by FACT-BP and KPS after receiving treatment via the STAT RT workflow.
- 2.1.3** Estimate patient satisfaction with the STAT RT workflow using a modified FACIT-TS-BTCSQ survey.
- 2.1.4** Report the treatment-related toxicity using CTCAE Version 4 and RTOG Late Radiation Morbidity Scoring Criteria after receiving treatment via the STAT RT workflow.

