## **3.0 PATIENT ELIGIBILITY**

### **3.1 Inclusion Criteria**

- 3.1.1** Patient has a biopsy proven diagnosis of cancer. The osseous metastatic lesions do not need to be biopsied.
- 3.1.2** Patients with multiple myeloma are eligible for the study.
- 3.1.3** Patient has 1-3 major painful osseous metastases (target lesions) from any primary cancer or unknown primary cancer.
- 3.1.4** Long bone target lesions must have a Mirels fracture score of  $\leq 7$  (See Appendix G).
- 3.1.5** Radiation oncologist determines that the patient is medically able to undergo palliative radiation therapy.
- 3.1.6** Patient has target lesions that are radiographically consistent with metastatic disease on CT, MR, or PET CT obtained within 8 weeks of treatment.
- 3.1.7** Persistent distinguishable pain associated with target sites to be treated.
- 3.1.8** Patient average BPI pain score for last 72 hours at specified location is  $\geq 3$  (0-10 scale)
- 3.1.9** Patients may have additional non-painful or minimally painful osseous metastases (if patient has pain from additional sites, the pain from the additional sites must be evaluated as being less intense by at least 2 points on the BPI compared to the site(s) treated)
- 3.1.10** The patient may have previously been treated with external beam radiation therapy to other body sites, but not to the target sites.
- 3.1.11** The patient may have previously or currently be undergoing chemotherapy or bisphosphonate therapy.

- 3.1.12** The patient will be able to understand English (or a medical interpreter for their native language must be available for all study visits).
- 3.1.13** 18 years of age or older.
- 3.1.14** Life expectancy > 12 weeks.
- 3.1.15** Able and willing to answer simple survey questionnaires.
- 3.1.16** Able and willing to keep a logbook of analgesic use (with or without assistance)
- 3.1.17** Willing to return to clinic at 4 weeks, 12 weeks, 6 months, and 12 months after treatment.
- 3.1.18** Signed study-specific informed consent form.
- 3.1.19** Women of childbearing potential and men must agree to use adequate contraception (hormonal or barrier method of birth control) prior to study entry and for the duration of study participation. Should a woman become pregnant or suspect she is pregnant while participating in this study, she should inform her treating physician immediately.

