#### **4.7 Duration of Follow Up**

After removal from study, patients will be followed for 12 months after treatment was initiated or until death, whichever occurs first. Patients removed from study for treatment-related adverse events will be followed until resolution or stabilization of the adverse event.

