### **5.4 Early Termination Visit**

Subjects may withdraw voluntarily from participation in the study at any time. At the time of withdrawal, the subject will be requested to provide their opioid logbook and complete the following surveys: BPI, FACT-BP/FACT-G, and Satisfaction survey.

Subjects may also withdraw voluntarily from receiving the study intervention for any reason. If that is the case, they will be encouraged to continue regular follow-up evaluations according to the Time and Events table.

As all of these patients have metastatic cancer and a limited life expectancy, it is likely that a reasonable percentage of study participants will choose hospice care before the completion of their follow-up.

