**1) Primary Aim: Evaluation of Outcomes of Patients with Osseous Metastases Treated with STAT RT**

We will recruit 30 cancer patients with 1-3 painful osseous metastatic lesions (target sites) requiring opioid medication who are candidates for palliative radiation therapy. Patients will receive 2-5 fractions of 5-10 Gy (minimum BED of 25 Gy) of conformal radiation therapy delivered to the target sites via the Helical TomoTherapy system using the STAT RT workflow. Patient pain, analgesic use, function, quality of life, and satisfaction will be recorded prior to treatment, at 1 week, 4 weeks, 8 weeks, 12 weeks, 6 months, and 12 months after therapy using the following measures:

- a) The Brief Pain Inventory (BPI)
- b) Patients will keep an analgesic use logbook and have their doses converted into Oral Morphine Equivalent Doses (OMED).
- c) Treatment response will be measured by the guidelines set forth by the International Bone Metastases Consensus Group as described in Section 6.1.1.
- d) The FACT-BP and FACT-G questionnaires
- e) Karnofsky Performance Scale (KPS)
- f) Patient Satisfaction will be measured by a modified FACIT-TS-BTCSQ survey.

Radiation-induced treatment related toxicities will be captured during treatment and at the above time points and graded using the CTCAE Version 4.0 and the RTOG Late Radiation Morbidity Score Criteria.

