### **7.3 Data Analyses Plans**

Treatment response as defined by International Bone Metastases Consensus Group will be determined for each patient. As described in Section 6.1.1, pain intensity as defined by the BPI and opiate use as quantified by the OMED will be used to categorize patients as having: Complete Response, Partial Response, Pain Progression, Stable Pain. At each evaluation, the patient's BPI and OMED at that visit will be compared to the pre-treatment levels. The "Worst Pain" score from the patient's BPI will be used to evaluate for treatment response. Patient response does not require a statistical analysis. The percentage of patients in each response category at each evaluation will be reported.

Patient pain will be recorded using the BPI before treatment and at designated evaluations after treatment. Pain scores before and after treatment will be compared using a Wilcoxon signed ranks test to determine if there is a statistically significant difference. Example: Pre-treatment vs. 1 week, Pre-treatment vs. 4 weeks, etc.

Analgesic use will be recorded by requiring each patient to keep a logbook of their analgesic intake. Their opiate intake for the last 72 hours will be converted to OMED at each evaluation and used in the categorization of treatment response. The difference between their OMED before and after treatment will be compared using paired two-sample t-tests.

Patients' functional status will be determined using the Karnofsky Performance Scale at each evaluation. The difference between the KPS before and after treatment will be compared using a Wilcoxon signed ranks test.

Patients' quality of life will be measured using FACT-BP and FACT-G scores at each evaluation. The difference between the FACT scores before and after treatment will be compared using a Wilcoxon signed ranks test.

Patient satisfaction will be measured using a modified version of FACT - TS – BTCSQ. No statistical analysis will be required for reporting the results. The average scores from the satisfaction survey will be reported.

To evaluate the CT detector dose calculations, the delivered radiation dose obtained using the phantom quality assurance will be compared to the exit radiation dose quality assurance calculation. The calculated dose and delivered dose for each patient will be compared using a paired two-sample t-test, and the % difference in dose will be reported.

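### KPS and FACT are tested against baseline at 6 and 12 months with no rule for death or non-assessment, so the late tests describe only patients alive and assessed and may lean toward better function and quality of life

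*Combined protocol and SAP*

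**What the plan says.** Objective 2.1.2, one of the primary objectives, is to "Estimate the change in the patient's quality of life and function as scored by FACT-BP and KPS" after treatment. Section 7.1 (Primary Aim) schedules the measures "prior to treatment, at 1 week, 4 weeks, 8 weeks, 12 weeks, 6 months, and 12 months after therapy using the following measures", and the Time and Events table in Section 5.1 marks KPS and both FACT surveys at 6 and 12 months.

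Section 7.3 has KPS and FACT scored at every evaluation and then names the test. For KPS: "The difference between the KPS before and after treatment will be compared using a Wilcoxon signed ranks test". For FACT: "The difference between the FACT scores before and after treatment will be compared using a Wilcoxon signed ranks test". It does not list the visits to be tested for these two measures. The paragraph on pain gives baseline against each visit in turn as its example, and that is the natural reading here too.

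Four other provisions bear on who will have a late score:
- Section 3.1.14 requires "Life expectancy > 12 weeks".
- Section 4.7 says "patients will be followed for 12 months after treatment was initiated or until death, whichever occurs first".
- Section 5.4 says "it is likely that a reasonable percentage of study participants will choose hospice care before the completion of their follow-up".
- Section 5.4 also asks withdrawing patients to "complete the following surveys: BPI, FACT-BP/FACT-G, and Satisfaction survey". KPS is not on that list, and no rule says how these surveys enter the analysis.

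Sections 7.1 to 7.3 define no analysis set, missing-data method, treatment of death or sensitivity analysis. Dropout is mentioned only in Section 7.2, as a reason for enrolling 30 when 21 are needed.

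**The concern.** A signed-rank test needs both values of each pair. With no rule for missing scores, a patient who has died or was not assessed simply drops out of that visit's test. Death and hospice entry plausibly go with falling function, which is what KPS and FACT measure, so loss may depend on the change being tested.

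Objective 2.1.2 asks about treated patients, while the late tests answer for those who remain. There is no control arm to reveal such selection, and the synopsis hypothesises improved quality of life. A significant 12-month improvement could partly reflect who was left to assess, and a real decline in the treated group could be missed.

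**Working it through.** **Inputs from the documents.** 30 patients; visits at weeks 1, 4, 8 and 12 and months 6 and 12; life expectancy above 12 weeks at entry. Section 7.2 (for BPI only): mean change 2, SD 3, two-sided alpha 0.05, 80% power, N = 21. Nothing comparable is given for KPS or FACT.

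**Step 1: the plan's own figure.** d = 2/3. For a signed-rank test with a normal parent, the effective n is 21 × 3/π = 20.05, and the noncentrality is (2/3) × √20.05 = 2.99. Power is 0.808 at N = 21 and 0.787 at N = 20, so 21 reproduces. The spare 30 − 21 = 9 patients (9/30 = 30%) protect power for the BPI effect. They do nothing about selection.

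**Step 2: how many pairs might remain.** The documents give no survival figure. Assuming exponential survival, the number alive is 30 × 0.5^(t/median):

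| Assumed median survival | Alive at 6 months | Alive at 12 months |
|---|---|---|
| 6 months | 15.0 | 7.5 |
| 9 months | 18.9 | 11.9 |
| 12 months | 21.2 | 15.0 |

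These counts are before any hospice loss or non-response. A loss of 40% (18 of 30 left) is therefore a plausible illustration, not a prediction.

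**Step 3: size of the bias in closed form.** Let p be the share observed and ρ the correlation between change and being observed. The mean change among those observed is then shifted by ρ × φ(z_p)/p, in units of the SD of change. At p = 0.6 this is 0.129, 0.193 and 0.322 SD for ρ = 0.2, 0.3 and 0.5. With an assumed KPS change SD of 15 points, that is 1.9, 2.9 and 4.8 points. It is zero when ρ = 0.

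**Step 4: effect on the test.** This was simulated with 30 patients, change distributed N(mean, 15) and a signed-rank test (normal approximation) on those observed. The log odds of being unassessed rise by a slope s for each SD of worsening relative to the group mean, and the intercept is set for 40% average loss. Slopes of 0.25, 0.5, 1 and 2 multiply the odds by 1.3, 1.6, 2.7 and 7.4 per SD.

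| Slope per SD | Bias, no true change (points) | Significant improvement, no true change | Significant worsening, true 10-point decline |
|---|---|---|---|
| 0 (random loss) | 0 | about 2.5% | about 73–74% |
| 0.25 | about +1.4 | about 5–6% | about 60% |
| 0.5 | about +2.9 | about 11–12% | about 49% |
| 1 | about +5.0 | about 29% | about 30% |
| 2 | about +7.3 | about 64% | about 15% |

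With no loss at all, power for the 10-point decline is about 93%. The fall from 93% to about 74% comes from having about 18 pairs instead of 30. Only the fall below about 74% is due to selection.

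**Step 5: a check on direction.** Suppose selection acts on baseline fitness alone (correlation 0.5 with being observed) and change is negatively related to baseline (correlation −0.3 or −0.5). The shift is then −0.07 to −0.20 SD at 70% and 50% observed, which is away from improvement. A bias toward better therefore requires selection on the patient's course, not merely fitter patients surviving.

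**The case against.** The strongest reply is that this is a 30-patient pilot with estimation objectives, and that change among survivors is a legitimate quantity to report. The protocol also limits avoidable loss. Section 5.4 requests FACT at withdrawal and encourages continued visits after treatment is stopped, and Sections 4.7 and 4.9 keep removed patients in follow-up. KPS is listed apart from the surveys, so inability to complete a questionnaire need not mean a missing KPS.

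Much of this is fair. These provisions reduce non-death loss, but they do not reach death, do not put KPS on the early-termination list and do not say how an early FACT value is used. Calling the trial a pilot does not remove the significance tests that Section 7.3 attaches to a primary objective. A survivors-only result is acceptable if it is labelled as one, and the plan does not do so.

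A reader might go further and infer that the late results are certainly biased upward, or that the remaining pairs are exactly the patients who did not decline. The documents do not support that. They give no percentage for hospice entry and no strength of selection. Patients who decline can still be assessed, and Step 5 shows a mechanism that works the other way. Upward is also the wrong word for FACT-BP, because most Appendix C items are worded so that a higher raw score is worse. Finally, Section 7.3 names a test and no estimator, so the bias concerns whatever change is reported beside it.

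The same gap affects the BPI and OMED comparisons. KPS and FACT are singled out because they measure the decline most likely to end assessment.

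**Conclusion.** The point stands as a defect in the stated analysis: followed as written, the 6- and 12-month tests of a primary objective use only patients alive and assessed, and the protocol itself expects such losses. That they may favour better function and quality of life is a reasonable inference, conditional on decline making assessment less likely.

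The size is illustrative. With 30 patients, an SD of 15 points and 40% loss, the bias is about +1.4 to +7.3 points for slopes of 0.25 to 2, and false improvement occurs in about 5% to 64% of trials. A true 10-point decline is detected in about 15% to 60% of trials, against about 74% if the same loss were random. If loss is unrelated to change, the bias is zero. The SD, loss rate and slopes are all assumptions. The sample size of 21 is not in question.

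**What to change.** In Section 7.3:

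1. Limit the KPS, FACT-BP and FACT-G significance tests to visits through week 12.
2. Report the 6- and 12-month changes descriptively, labelled *among patients alive and assessed*, with no claim of improvement for the treated group.
3. At each visit, report the numbers alive and assessed, and baseline KPS and FACT for patients with and without a score.

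Ranking patients who died or were too ill as having the worst change, and then running the signed-rank test, is tempting but should not be adopted. In a single arm it becomes largely a mortality count. With loss unrelated to change and no true change in survivors, it declares worsening in about 41%, 92% and 99.9% of trials at 20%, 40% and 60% loss.

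The cost is a wording change, one extra table and no late p-values. No additional patients or visits are needed.

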## **STUDY OVERVIEW**

- Eligible patients with 1-3 painful osseous metastases will receive a consultation and subsequently undergo CT simulation, radiation treatment planning, and their first radiation treatment on day 1.
- Patients will receive a total of 2-5 fractions of high dose palliative radiation therapy via helical TomoTherapy consisting of 5-10 Gray (Gy) per fraction with a minimum biologic effective dose (BED) of 25 Gy.
- Standard patient-specific treatment planning quality assurance will be performed on a cylindrical phantom with ion chamber and film measurement.
- Software provided by TomoTherapy Inc.® will be used to measure the radiation exiting the patient and recalculate the dose the patient received. This calculated dose will then be compared to phantom measurements and treatment planning calculations to validate the ability of this novel radiation dose verification software to verify the accurate delivery of radiation. This will not replace standard quality assurance measurements.
- At the Emily Couric Cancer Center, an in-house developed infrared motion tracking system will monitor patients' positions for any deviation from the treatment position. This is not standard of care but may augment standard safety measures with full implementation in the future and does not subject the patient to any risks or discomfort. Infrared motion tracking is will be optional and not required for patients treated at CRH.
- Contouring (the demarcation of the tumor and critical structures) will be performed in the standard manner for treatment planning.
- Contouring will also be performed in an expedited, experimental manner on diagnostic image sets which will then be compared to the standard contours. Experimental contouring will not replace standard contouring, nor affect treatment planning.
- Patients will complete questionnaires to capture pain scores of the treated lesion(s), analgesic use, patient functional status, patient quality of life, and patient satisfaction at 1 week, 4 weeks, 8 weeks, 12 weeks, 6 months, and 12 months following treatment. These scores will be compared to questionnaires completed pretreatment.
- Radiation-induced toxicities will be captured during treatment physical examinations and at follow-up physical examinations at 4 weeks, 12 weeks, 6 months, and 12 months.

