## **5.0 EVALUATIONS AND ASSESSMENTS**

### **5.1 Time and Events Table**

|  | Pre-treatment | During treatment | Week 1 | Week 4 | Week 8 | Week 12 | 6-Month | 12-Month |
|--|----------------------|-------------------------|---------------|---------------|---------------|----------------|----------------|-----------------|
| Informed Consent                                   | X                    |                         |               |               |               |                |                |                 |
| History and PE                                     | X                    |                         |               | X             |               | X              | X              | X               |
| Karnofsky Performance Status                       | X                    |                         | X             | X             | X             | X              | X              | X               |
| Toxicity Evaluations                               |                      | X                       | X             | X             | X             | X              | X              | X               |
| Opiod Logbook Evaluation                           | X                    | X                       | X             | X             | X             | X              |                |                 |
| Brief Pain Inventory                               | X                    |                         | X             | X             | X             | X              | X              | X               |
| FACT-BP and FACT-G surveys                         | X                    |                         | X             | X             | X             | X              | X              | X               |
| Satisfaction and Convenience Survey                | X                    |                         | X             | X             | X             | X              | X              | X               |
| Quality Assurance                                  | X                    |                         |               |               |               |                |                |                 |
| Diagnostic Imaging (CT/MRI/PET CT)                 | X                    |                         |               |               |               |                |                |                 |

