## **APPENDIX D**

### **Bone Treatment Convenience and Satisfaction Questionnaire** **FACIT-TS-BTCSQ – Baseline (Modified)**

For each statement, please choose the response that best describes your expectation of this treatment.

"Treatment for bone disease" means the radiation you receive to treat your bone disease only, NOT your other cancer treatments.

| Treatment for Bone Disease Expectations  | Not at All | A little bit | Some-what | Quite a bit | Very much |
|---|-------------------|---------------------|------------------|--------------------|------------------|
| I believe that my treatment for bone disease will cause me physical pain .....                    | 0                 | 1                   | 2                | 3                  | 4                |
| I believe that receiving treatment for bone disease will be inconvenient. ....                    | 0                 | 1                   | 2                | 3                  | 4                |
| I worry that my treatment for bone disease will not be effective. ....                            | 0                 | 1                   | 2                | 3                  | 4                |
| I believe that treatment for bone disease will be harmful to me. ....                             | 0                 | 1                   | 2                | 3                  | 4                |
| I believe that my treatment schedule for bone disease will be stressful to me . ....       | 0                 | 1                   | 2                | 3                  | 4                |
| I believe that my treatment schedule for bone disease will be stressful to my family ..... | 0                 | 1                   | 2                | 3                  | 4                |
| I believe that I will be bothered by side effects of treatment for bone disease .....             | 0                 | 1                   | 2                | 3                  | 4                |

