## APPENDIX E

### Bone Treatment Convenience and Satisfaction Questionnaire FACIT-TS-BTCSQ – On Treatment (Modified)

#### The following to be completed by patient.

The following is a list of statements that people receiving bisphosphonate therapy have commented are important. For each statement, please choose the response that best describes your expectation of this treatment.

**"Treatment for bone disease"** means the drug(s) you receive to treat your bone disease only, NOT your other cancer treatments.

| Treatment for Bone Disease Expectations                                | Not at All | A little bit | Some-what | Quite a bit | Very much |
|--|------------|--------------|-----------|-------------|-----------|
| Treatment for bone disease takes up my time .....               | 0          | 1            | 2         | 3           | 4         |
| My treatment for bone disease takes up my family's time .....   | 0          | 1            | 2         | 3           | 4         |
| I worry about side effects from treatment for bone disease.....        | 0          | 1            | 2         | 3           | 4         |
| My treatment for bone pain causes me physical pain .....               | 0          | 1            | 2         | 3           | 4         |
| Receiving treatment for bone disease is inconvenient. ....             | 0          | 1            | 2         | 3           | 4         |
| I worry that my treatment for bone disease will not be effective. .... | 0          | 1            | 2         | 3           | 4         |

|  |   |   |   |   |   |
|--|---|---|---|---|---|
| Treatment for bone disease seems harmful to me. ....                             | 0 | 1 | 2 | 3 | 4 |
| My treatment schedule for bone disease is
stressful to me .....        | 0 | 1 | 2 | 3 | 4 |
| My treatment schedule for bone disease is
stressful to my family ..... | 0 | 1 | 2 | 3 | 4 |
| I am bothered by side effects of treatment for
bone disease.                  | 0 | 1 | 2 | 3 | 4 |

Considering your experience with treatment for bone disease to date, please respond to the following questions.

|  | No, not
at all | Yes, to
some
extent | Yes, for
the most
part | Yes,
completely |
|--|---------------------------|------------------------------------|---------------------------------------|----------------------------|

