| Are you satisfied with the results of the treatment for
your bone disease so far? ..... | 0                         | 1                                  | 2                                     | 3                          |

|   | No | Maybe | Yes |
|---|-----------|--------------|------------|
| Would you recommend this treatment for bone
disease to others with your illness? ..... | 0         | 1            | 2          |
| Would you choose this treatment for bone disease
again? .....                          | 0         | 1            | 2          |

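### Satisfaction (objective 2.1.3) is to be reported as average scores with no scoring rule, on a follow-up form that mixes item directions and ranges and matches the baseline form on only seven of 13 items

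*Combined protocol and SAP*

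**What the plan says.** Objective 2.1.3 (Section 2.1) is to "Estimate patient satisfaction with the STAT RT workflow using a modified FACIT-TS-BTCSQ survey". Sections 1.1 and 1.5 hypothesise that satisfaction will be high.

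Section 7.3 says of this outcome: "No statistical analysis will be required for reporting the results", and then "The average scores from the satisfaction survey will be reported". It gives no reverse-coding, rescaling or subscale rule, and none appears elsewhere in the document. Section 1.5 says the study team adapted the instrument to its own patients.

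The Study Overview lists satisfaction among the post-treatment questionnaires and adds: "These scores will be compared to questionnaires completed pretreatment". The "Satisfaction and Convenience Survey" row in Section 5.1 schedules the form before treatment and at all six follow-up times.

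Two versions are printed. The baseline version (Appendix D) asks about expectations, for example "I believe that receiving treatment for bone disease will be inconvenient". The on-treatment version (Appendix E) has burden items such as "Receiving treatment for bone disease is inconvenient", followed by three direct questions, the first beginning "Are you satisfied with the results of the".

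**The concern.** The descriptive average is the only answer the plan offers to a primary objective, so it has to be interpretable. On the follow-up form a high score means burden on ten items and approval on three, and the items use three different ranges. Averaged as they stand, the answers that bear most directly on satisfaction pull the score the same way as greater burden.

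The Study Overview's comparison with pretreatment raises a second problem. The two forms do not contain the same items, and the baseline form contains no satisfaction question. A difference between their averages therefore mixes change in the patient with change in the questionnaire.

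**Working it through.** The documents state no numerical figure for satisfaction, so there is nothing to reproduce. The check is a count of items, directions and ranges on the printed forms, followed by score arithmetic on hypothetical patients. Appendix E is taken as the follow-up form because it is the only post-baseline version printed. The resource-use tables that follow it are not counted.

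**Step 1. Item inventory (Appendices D and E).**

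| Block | Baseline (D) | Follow-up (E) | Range | High means |
|---|---|---|---|---|
| Burden, matching items | 7 | 7 | 0–4 | bad |
| Burden, new items (own time, family's time, worry about side effects) | 0 | 3 | 0–4 | bad |
| Satisfied with results | 0 | 1 | 0–3 | good |
| Would recommend; would choose again | 0 | 2 | 0–2 each | good |
| Total | 7 | 13 | | |

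The seven matching topics are physical pain, inconvenience, worry about effectiveness, harm, schedule stress to self, schedule stress to family, and being bothered by side effects. Follow-up items without a baseline counterpart: 13 − 7 = 6, namely three burden items and all three satisfaction items.

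**Step 2. Weight of the satisfaction items if raw scores are pooled.** Maximum raw total = 10×4 + 3 + 2 + 2 = 47. The satisfaction items supply 3 + 2 + 2 = 7, and 7/47 = 14.9%.

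**Step 3. Pooled raw mean = (burden sum + satisfaction sum)/13.**

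- No burden, fully satisfied: (0 + 7)/13 = 0.54
- No burden, fully dissatisfied: (0 + 0)/13 = 0.00
- Maximum burden, fully dissatisfied: (40 + 0)/13 = 3.08
- Maximum burden, fully satisfied: (40 + 7)/13 = 3.62

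If low is read as good, the dissatisfied patient without burden beats the satisfied one. If high is read as good, the most burdened patients score best. Neither reading orders the four patients correctly.

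**Step 4. Pooled mean against the baseline mean.** Take a patient who scores 1 on every burden item on both forms. Baseline: 7/7 = 1.00. Follow-up if fully satisfied: (10 + 7)/13 = 1.31. Follow-up if fully dissatisfied: 10/13 = 0.77. Read in the burden direction, satisfaction looks like worsening and dissatisfaction like improvement, although no matching item has changed.

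**Step 5. The two blocks kept apart, each rescaled to 0–100 with high good.** Burden = 100×(1 − mean/4). Satisfaction = mean of 100×(answer/item maximum). The four patients in Step 3 become, as burden/satisfaction, 100/100, 100/0, 0/0 and 0/100. The order is now correct within each block.

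**Step 6. What the forms ask about.** Appendix D defines the treatment in question as radiation. Appendix E is introduced as a list drawn from people on bisphosphonate therapy, defines the treatment as drugs, and tells the patient to answer by expectation. Read literally, the two forms concern different treatments, and the follow-up form does not ask about experience.

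**The case against.** A reader might infer that the plan commits to a pooled 13-item mean. It does not. Section 7.3 speaks of scores in the plural and names no total or composite, so a mean for each item or block is an equally natural reading. On that reading the mixed directions and ranges do no harm at follow-up, and the figures in Steps 2 to 4 do not arise. That part of the objection stands.

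The form also derives from a cited published instrument whose scoring guidance is not reproduced here. The protocol prints FACT-G (Appendix B), which also mixes directions, without a scoring rule either. So the omission does not show that raw pooling is intended. But the satisfaction form was modified by the study team, and Section 7.3 refers to no scoring source for the modified version.

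A reader might also infer that a before/after test of satisfaction is planned. Section 7.3 plans such tests for pain, opioid dose, performance status and quality of life, but none for satisfaction. Objective 2.1.3 is to estimate a level, whereas 2.1.2 is to estimate a change. The comparison rests on a general sentence in the Study Overview. What remains is a conflict between the two sections and a comparison that, if made on form averages, could not be interpreted.

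Finally, this is a 30-patient pilot with descriptive reporting, and no decision rule uses this score. That limits the consequence. It does not remove the need for an interpretable number.

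**Conclusion.** The concern holds in a limited form. A primary objective is to be summarised by averages whose construction is not stated, on a form where one plausible construction misorders patients. The size is 0.54 against 0.00 for fully satisfied and fully dissatisfied patients without burden, and it applies only if raw items are pooled. The shift from 1.00 to 1.31 or 0.77 is likewise conditional on pooling, and it is not shown to be the planned analysis. All patient scores here are illustrations, not trial data.

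The mismatch between forms does not depend on pooling. Six of 13 follow-up items have no baseline value, including every satisfaction item. Even on the seven matching items, the two forms as printed refer to different treatments.

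It would go too far to say that objective 2.1.3 cannot be answered. The three direct questions are asked at follow-up and can answer it if they are reported separately and the form clearly refers to the radiation. This should be corrected. It does not affect the pain endpoint or safety.

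**What to change.** 1. In Section 7.3, state that no pooled 13-item mean will be used. Report the three satisfaction items (satisfied with results, would recommend, would choose again) separately, as the percentage giving each answer or as item-level summaries with the direction stated. Report a burden score from the ten 0–4 items, all in one direction.
2. Reconcile the Study Overview with Section 7.3. Limit any baseline comparison to the seven matching items and describe it as experience against expectation.
3. Correct the Appendix E instructions so that they refer to the patient's experience of the radiation treatment, in line with Appendix D, instead of drugs, bisphosphonate therapy and expectation.

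The cost is a few sentences of analysis wording, a small correction to the form's text, and the loss of any single headline satisfaction score. No extra patients, visits or items are needed.
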